enter the arterial lumen at the distal reconstitution site, leaving only a small portion of a stented graft inside of the native artery and bypassing the heavily diseased area. Using the same synthetic materials to surgically bypass lesions yields an average 12-month primary patency of 80%.^{39, 45, 49, 50, 51, 52, 53, 54, 55}

The PQ Bypass approach to treating long-segment disease also takes advantage of the reduced risk associated with endovascular repair compared with surgery. In reviewing the literature on traditional endovascular techniques (e.g., PTA, stents and stent grafts), very little information on co-morbidities can be identified. The majority of the safety concerns cited are related to the need for re-intervention. In fact, one recent study looking at the safety of stent graft use at one study center looked specifically for the use of thrombolysis (for occlusions) and the need for amputation and bypass surgery as their primary endpoint.⁵⁶ Restenosis or thrombosis of the target lesion/stent/stent graft requires the patient be exposed to another interventional procedure which carries some degree of safety concerns. These include, but are not limited to: access site hemorrhage or hematoma, access site pain, acute vessel closure, embolism, infection, and renal insufficiency/failure due to excessive contrast load.

Patients undergoing endovascular repair are often discharged from the hospital the next day whereas surgically treated patients may stay in the hospital for up to 7 days. Endovascularly treated patients can often go back to normal activities within the first week following the procedure. Surgically treated patients can take 6 weeks or longer to fully recover^{56,57}. These extended recovery times combined with increasingly positive patency findings, are the principle reasons behind the previously cited decline in surgery and rise of endovascular repairs in recent years.

PQ Bypass seeks to place stent grafts in bypass conduit via a percutaneous method to evaluate the bypass concept as it compares to standard stent graft placement.

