11.0 ENDPOINTS AND STATISTICAL ANALYSIS PLAN

11.1 Endpoints Analyses and Reporting of Results

The study objective is to assess the safety and performance of the PQ Bypass System to access, deliver guidewires and implant stent grafts for a percutaneous fem-pop bypass.

The study is a feasibility study with no formal hypothesis testing and therefore no required sample size. Study results will be presented using descriptive statistics. Results from this study will be used to design additional clinical studies.

All subjects will be followed on an intent-to-treat basis. The device performance will be assessed based on a per-protocol analysis of the primary safety and effectiveness endpoints. An Intent-to-treat analysis, along with other secondary analyses, will also be completed and reported.

Demographic, baseline clinical and disease characteristics, procedural results and primary, secondary and all additional endpoints will be summarized using descriptive statistics.

All statistical analyses will be performed using SAS for Windows version 9.1 or higher.

Primary Safety Endpoint Reporting:

Safety assessment is achieved by recording and measuring Major Complication rates/Serious Adverse Event rates associated with the PQ Bypass procedure. The number and percentage 6-month MAE will be presented using descriptive Statistics. Using the Score approximation, the one-sided upper 95% confidence bound will be calculated and presented.

Primary Performance Endpoint Reporting:

Descriptive statistics of the primary performance endpoint which includes total number of patent PQB grafts, number and percentage of patent PQB grafts, and the one-sided 95% CI of the percentage using the Score approximation will be presented. The lower bound of the one-sided 95% CI will be compared to the performance goal of 70% (80% historical control rate – 10% Delta.)

Secondary Endpoint Analysis:

The secondary endpoint of primary assisted and secondary patency will be summarized using Kaplan-Meier survival analysis. Life tables will be created and a Kaplan-Meier survival curve will be presented.

The secondary endpoints of Procedural Success, Clinical Success and Technical

Success will be summarized by providing point estimates, number of subjects, and 95% confidence bounds calculated using the Score approximation.

Demographic, procedural and safety data:

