Methods: From March 2004 to May 2005, 100 limbs in 86 patients with femoropopliteal arterial occlusive disease were identified. Patients had symptoms ranging from claudication to rest pain, with or without tissue loss, and were prospectively randomized for treatment into one of two groups. The limbs were treated percutaneously with angioplasty and one or more self-expanding stent grafts (n=50) or surgically with femoral-to-AK popliteal artery bypass using synthetic Dacron or ePTFE grafts (n=50).

The mean and SD total length of artery stented was 25.6 and 15 cm. Follow-up evaluation with ankle-brachial indices and color flow duplex sonography imaging were performed at 3, 6, 9, and 12 months after treatment.

Patients were monitored for a median of 18 months. No statistical difference was found in the primary patency (P=895) or secondary patency (P=.861) between the two treatment groups. Primary patency at 3, 6, 9, and 12 months of follow-up was 84%, 82%, 75.6%, and 73.5% for the stent graft group and 90%, 81.8%, 79.7%, and 74.2% for the femoral-popliteal surgical group. Thirteen patients in the stent graft group had 14 re-interventions, and 12 re-interventions occurred in the surgical group. This resulted in secondary patency rates of 83.9% for the stent graft group and 83.7% for the surgical group at the 12-month follow-up (**Table 11-2**).

Based on review of the limited literature and the recent long lesion stent graft vs prosthetic surgery randomized study 6-month surgical bypass primary patency rate of 82-85% can be extrapolated.

Table 11-2 Randomized Comparison of Viabahn Stent Graft vs. Prosthetic Surgery

Table IV. Primary patency in femoral-popliteal bypass group and stent graft group

Time post-treatment (months)	N at risk at start of interval	N events during interval*	N censored during interval*	% Free from loss of patency	95% CI
Operative (day 0-30)					
Fem-pop bypass	50	2 (2)	0 (0)	0.960	(0.849, 0.990)
Stent graft	50	2 (2)	0 (0)	0.960	(0.849, 0.990)
3 months (day 31-136)					
Fem-pop bypass	48	3 (5)	1 (1)	0.900	(0.776, 0.957)
Stent graft	48	6 (8)	1 (1)	0.840	(0.705, 0.917)
6 months (day 137-227)					
Fem-pop bypass	44	4 (9)	2 (3)	0.818	(0.680, 0.901)
Stent graft	41	1 (9)	1 (2)	0.820	(0.682, 0.902)
9 months (day 228-319)					
Fem-pop bypass	38	1 (10)	8 (11)	0.797	(0.655, 0.885)
Stent graft	39	3 (12)	1 (3)	0.756	(0.611, 0.854)
12 months (day 320-456)					
Fem-pop bypass	29	2 (12)	8 (19)	0.742	(0.587, 0.846)

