Stent graft	35	1 (13)	7 (10)	0.735	(0.587, 0.837)

CI, Confidence interval.

Log-rank $P = .895$.

*Number in parenthesis represents cumulative events or censored observations through end of interval.

Table V. Secondary patency in femoropopliteal bypass group and stent graft group

Time post-treatment (months)	N at risk at start of interval	N events during interval*	N censored during interval*	% Free from loss of patency	95% CI
Operative (day 0-30)					
Fem-pop bypass	50	2 (2)	0 (0)	0.960	(0.849, 0.990)
Stent graft	50	0 (0)	0 (0)	1.000	(1.000, 1.000)
3 months (day 31-136)					
Fem-pop bypass	48	2 (4)	1 (1)	0.920	(0.801, 0.969)
Stent graft	50	6 (6)	1 (1)	0.880	(0.752, 0.944)
6 months (day 137-227)					
Fem-pop bypass	45	3 (7)	2 (3)	0.859	(0.726, 0.930)
Stent graft	43	1 (7)	1 (2)	0.860	(0.728, 0.930)
9 months (day 228-319)					
Fem-pop bypass	40	1 (8)	8 (11)	0.837	(0.701, 0.915)
Stent graft	41	1 (8)	1 (3)	0.839	(0.703, 0.916)
12 months (day 320-456)					
Fem-pop bypass	31	0 (8)	11 (22)	0.837	(0.701, 0.915)
Stent graft	39	0 (8)	9 (12)	0.839	(0.703, 0.916)

CI, Confidence interval.

Log-rank P value = .861.

*Number in parenthesis represents cumulative events or censored observations through end of interval.

Kedora et al J Vasc Surg 2007;45:10-16

McQuade et al J Vasc Surg. 2009 Jan;49(1):109-15

In order to establish a sample size, a margin of non-inferiority, delta, was set at 10% for the current study to demonstrate non-inferiority of the PQ Bypass Systems to the historical control in terms of patency. This delta reflects the limited quantitative and qualitative availability of fem-pop bypass studies in the literature. Therefore, a 10% delta is adequate to accurately reflect non-inferiority. This delta sets up a comparison between the lower 95% CI of the PQ Bypass Systems performance to the lower 95% CI reported for the competitive products (~70%).

As such using as historical control rate of 80-85% and a non-inferiority margin of 10%, the null and alternative hypotheses of the primary performance endpoint can be written as:

$$H_0: \pi_{PQB_performance} \leq \pi_{PG_performance}$$

$$H_A: \pi_{PQB_performance} > \pi_{PG_performance}$$

where,

$$\pi_{PG_performance} = 85\% \text{ historical control rate} - 10\% \text{ Delta}$$

$$\pi_{PQB_performance} = \text{PQB Systems success rate}$$

The hypotheses for the primary performance endpoint can be rewritten as:

$$H_0: \pi_{PQB_performance} \leq 70\%$$

$$H_A: \pi_{PQB_performance} > 70\%$$

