A conservative estimate of 85% performance for the PQ Bypass Systems was utilized along with the aforementioned performance goal for the purpose of sample size estimation. To achieve 80% power using a one-sided alpha of 0.05, the maximum sample size required is 103 subjects. As the surgical patency rate is extrapolated to be between 82% and 85% and since no loss to follow-up is expected in the study, a sample size of 100 subjects should be sufficient and enrolled in this study (**Table 11-3**).

Table 11-3: Non-Inferiority with PQ Bypass Performance of 85%

PG	NI Margin				
	5%	7.5%	10%	12.5%	15%
80%	103	69	50	38	30
85%	368	174	103	69	50
90%	-	1371	368	174	103
95%	-	-	-	1371	368

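### The surgical comparison was sized for a 75% goal but is tested at 70%, so a pass supports the stent-graft claim and not non-inferiority to prosthetic bypass

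*Combined protocol and SAP*

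**What the plan says.** Section 11.2 sets up two comparisons, both with a 10-point margin.

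- **Stent grafts (60 subjects).** The 6-month control is 80%, so the goal is 70%.
- **Prosthetic surgical bypass (100 subjects).** The larger number is justified on the ground that surgical results are better than those of stent grafts. From limited literature and one randomized study, the section says a "6-month surgical bypass primary patency rate of 82-85% can be extrapolated". That study's patency at 3, 6, 9 and 12 months is quoted as "90%, 81.8%, 79.7%, and 74.2% for the femoral-popliteal surgical group". The hypotheses are then introduced with "As such using as historical control rate of 80-85% and a non-inferiority margin of 10" per cent. The goal is defined as 85% less 10%, but the next lines write the null as 70%.

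On size, section 11.2 says "A conservative estimate of 85% performance for the PQ Bypass Systems was utilized" and "To achieve 80% power using a one-sided alpha of 0.05, the maximum sample size required is 103 subjects". It then treats 100 as sufficient.

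Section 11.1 gives one decision rule for the primary performance endpoint: "The lower bound of the one-sided 95% CI will be compared to the performance goal of 70% (80% historical control rate – 10% Delta").

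Section 2.2 gives a further surgical figure as background: "Using the same synthetic materials to surgically bypass lesions yields an average 12-month primary patency of 80" per cent.

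**The concern.** The surgical comparison is the stated reason for going from 60 to 100 subjects, yet it ends at the same 70% null as the stent-graft comparison. With a 10-point margin, 70% corresponds to a 6-month surgical control of 80%. That value fits none of the protocol's other surgical figures well:

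- It is below the randomized study's 81.8% at 6 months and below the 82-85% range drawn from it.
- It is 5 points below the 85% used for the 103 subjects.
- It equals the 12-month surgical average in section 2.2. Since primary patency cannot recover, the two together would mean no loss between months 6 and 12. Table 11-2 shows surgery losing 81.8 - 74.2 = 7.6 points over that time.

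At stake is what a pass means. A lower bound just above 70% meets the only rule in section 11.1 and could be reported as non-inferiority to surgery, although the sample was sized for a stricter goal.

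**Working it through.** **Inputs.** One-sided alpha 0.05, 80% power and true device patency 85% (11.2); goals of 70% (11.1 and the written null in 11.2) and 75% (85% less 10%, 11.2); one-sided 95% Score bound (11.1). N = 100 is taken as fully evaluable, because 11.2 expects no loss to follow-up.

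**1. Reproduce the plan's sizes.**

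n = [1.645·√(p0(1-p0)) + 0.842·√(p1(1-p1))]² / (p1-p0)², with p1 = 0.85.

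- p0 = 0.70: n = 49.4, so 50 as printed.
- p0 = 0.75: n = 102.6, so 103 as printed.

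Every cell of Tables 11-1 and 11-3 reproduces. The 103 therefore belongs to a 75% goal; at 70% the plan's own formula needs 50.

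**2. Passing counts at N = 100.** The Score lower bound exceeds p0 when (x/100 - p0)/√(p0(1-p0)/100) > 1.645.

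| Goal | Count just failing (z) | First passing count (z) |
|---|---|---|
| 70% | 77 (1.53) | 78 (1.75) |
| 75% | 82 (1.62) | 83 (1.85) |

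Results of 78 to 82 patent grafts pass at 70% and fail at 75%.

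**3. Chance that a device exactly 10 points below surgery passes the 70% rule**, P(X ≥ 78), X ~ Bin(100, p):

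| Surgical 6-month rate | Device p | P(pass) |
|---|---|---|
| 80% | 70% | 4.8% |
| 81.8% (randomized study) | 71.8% | 10% |
| 82% | 72% | 11% |
| 85% (used for sizing) | 75% | 29% |

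With the pass mark at 83, the device at 75% passes 3.8% of the time.

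**4. Power at N = 100, true patency 85%.**

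| Goal | Plan's formula | Exact, Score rule |
|---|---|---|
| 70% | 98% | 98% |
| 75% | 79% | 76% |

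The plan attaches 80% power to 103 subjects, not to 100.

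**5. Sensitivity to the 12-month average.** Five ways of carrying 80% at 12 months back to 6 months, four of them using Table 11-2's 81.8% and 74.2%:

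- Same ratio of failures: 1 - 0.20 × (0.182/0.258) = 85.9%
- Proportional hazards: 0.80^(ln 0.818/ln 0.742) = 86.1%
- Same point loss: 0.80 + 0.076 = 87.6%
- Same ratio of patency: 0.80 × 0.818/0.742 = 88.2%
- Constant hazard (Table 11-2 not used): √0.80 = 89.4%

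Less 10 points, the goals are 75.9% to 79.4%. Exact power at N = 100 then runs from 76% down to 35%, and the plan's formula needs about 121 to 302 subjects for 80% power. So 103 is a maximum only if the surgical control is at most 85%.

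**The case against.** A reader might go further and infer that the 80% average at 12 months contradicts the 82-85% range, that it implies about 88% at 6 months, and hence that the goal should be 78% and the power is 57%. The documents do not support this, for four reasons.

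- **No contradiction.** A fall from 82-85% at 6 months to 80% at 12 months is a loss of 2 to 5 points, which is possible. In Table 11-2 surgery lost only 2.1 points between 6 and 9 months (81.8% to 79.7%). Only the 80% end of the range would require no loss at all.
- **The carry-back is weak.** Apart from constant hazard, it rests on three surgical losses after month 6 (1 of 38 at risk, then 2 of 29). Patency at 12 months given patency at 6 is (37/38)(27/29) = 0.907, with a 95% interval of about 0.735 to 0.97 (Greenwood, log-log). The upper limit, 0.9695 before rounding, gives 0.80/0.9695 = 82.5% at 6 months, inside the protocol's range.
- **The choice of source is explained.** Section 11.2 calls the surgical literature limited, notes that few studies used duplex velocity criteria, and prefers the randomized study. Its 81.8% (95% CI 68.0% to 90.1%) is the only direct 6-month surgical estimate in the documents. The 12-month average is background and does not enter section 11.
- **The written test does not depend on the surgical rate.** Against 70%, power at N = 100 is about 98% whatever surgery achieves.

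All four stand, and they dispose of the stronger reading. They do not remove the gap between the 75% used for sizing and the 70% used for testing; the last one shows that the test passes easily without addressing the surgical question.

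It may also be said that section 11.1 calls this a feasibility study without formal hypothesis testing. That lowers the stakes. But 11.2 gives non-inferiority as the reason for the sample size and 11.1 compares the bound with a goal, so the meaning of a pass still needs stating.

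**Conclusion.** The point holds as a mismatch within sections 11.1 and 11.2. The goal of 85% less 10% is 75%, and 103 subjects fit that goal; the written null and the decision rule use 70%. Under the 70% rule, a device exactly 10 points below surgery passes about 10% of the time if surgery is at 81.8% and about 29% if it is at 85%, against a nominal 5%. A pass at 70% therefore supports the stent-graft goal but not non-inferiority to prosthetic bypass. These figures assume 100 evaluable subjects, the Score rule as written, and the protocol's own control rates and margin.

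The relation between the 12-month average of 80% and the 82-85% range at 6 months is a secondary gap: unexplained, but not an inconsistency in itself. The 86-89% obtained by carrying the average back is a sensitivity range under stated assumptions. Neither 88%, nor a 78% goal, nor 57% power is implied by the documents.

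**What to change.** 1. In 11.1 and 11.2, tie the 70% goal to the stent-graft comparison only.
2. In 11.2, correct the surgical null to 75%. In 11.1, allow a statement of non-inferiority to prosthetic bypass only if the one-sided 95% Score lower bound exceeds 75% (83 of 100 or more patent).
3. Restate power for the surgical comparison at N = 100 and 85% true patency as about 76% (exact Score rule) or 79% (the plan's formula).
4. In 11.2, say how the 12-month average of 80% in section 2.2 relates to the 82-85% range. Either state that it is not comparable and why, or add the sensitivity range: about 86-89% at 6 months, goals of about 76-79%, exact power from about 76% down to 35%. In either case, say that 103 is a maximum only for a control of at most 85%.

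This changes wording and adds one comparison of a bound that is already planned; it needs no further subjects or data. The price is a slightly less favourable stated power and a harder bar for the surgical claim.

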11.2 Sample Size Justification

The sample size chosen for this study has been updated from 60 to 100 patients. The sample size was chosen to demonstrate statistically non-inferiority of the PQ Bypass Systems performance as compared to results previously reported in similar studies:

- for intravascular stent grafts (e.g. Gore Viabahn) – n=60
- for prosthetic surgical bypass - n=100

A larger sample size is required as prosthetic surgical bypass outcomes are superior to those of intravascular stent grafts.

Stent Graft Studies

Clinical data published on existing stent graft techniques for treating femoropopliteal disease have reported 6-month primary patency rates of approximately 80%.^{37,40-42,45,60,61} This average success rate has been used as the historical control for the current study. The standard error reported in the cited studies range from 3% to 12%; the lower limit of one-sided 95% confidence intervals (CI) is approximately 68%.

In order to establish a sample size, a margin of non-inferiority, delta, was set at 10% for the current study to demonstrate non-inferiority of the PQ Bypass Systems to the historical control in terms of patency. This delta reflects the diversity of the lesions to be enrolled in this study and the range of reported performance using similar technology; 6-month primary patency in the studies cited above ranges from 27% to 92%, average lesion lengths range from 9-25cm and the percent occlusions included ranges from 50% to 100%. Due to this wide variety of lesions reported in the literature and the potential diversity of patients and lesion lengths that will be enrolled in this study, a 10% delta is adequate to accurately reflect non- inferiority. This delta sets up a comparison between the lower 95% CI of the PQ Bypass Systems performance to the lower 95% CI reported for the competitive products (~70%).

As such using as historical control rate of 80% and a non-inferiority margin of 10%,

the null and alternative hypotheses of the primary performance endpoint can be written as:

$$H_0: \pi_{PQB_performance} \leq \pi_{PG_performance}$$

$$H_A: \pi_{PQB_performance} > \pi_{PG_performance}$$

where,

$$\pi_{PG_performance} = 80\% \text{ historical control rate} - 10\% \text{ Delta}$$

$$\pi_{PQB_performance} = \text{PQB Systems success rate}$$

The hypotheses for the primary performance endpoint can be rewritten as:

$$H_0: \pi_{PQB_performance} \leq 70\%$$

$$H_A: \pi_{PQB_performance} > 70\%$$

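### Passing the fixed 70% goal shows that patency exceeds 70%; it does not show non-inferiority to surgical bypass within 10 points, which Section 11.2 gives as the purpose of the sample size

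*Combined protocol and SAP*

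**What the plan says.** Section 11.2 opens with the purpose: "The sample size was chosen to demonstrate statistically non-inferiority of the PQ Bypass Systems performance" relative to earlier studies, with n=60 for the intravascular stent-graft comparison and n=100 for prosthetic surgical bypass.

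For surgery, the only outcome data shown are the bypass arm of one randomized study (Table 11-2): 50 limbs, 6-month primary patency 0.818, 95% CI 0.680 to 0.901. From these and a literature review the plan extrapolates 82-85%. It then adopts a "historical control rate of 80-85% and a non-inferiority margin of 10" points. Two reasons are given for the margin. One is that "This delta reflects the limited quantitative and qualitative availability of fem-pop bypass studies in the literature". The other is put as follows: "comparison between the lower 95% CI of the PQ Bypass Systems performance to the lower 95% CI reported for the competitive products (~70"%).

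The formula for the goal is 85% minus 10%, but the hypotheses are then rewritten with 70%. The stated size is: "To achieve 80% power using a one-sided alpha of 0.05, the maximum sample size required is 103 subjects".

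Section 11.1 gives the operative rule: "The lower bound of the one-sided 95% CI will be compared to the performance goal of 70"%, described there as an 80% historical rate less 10%. The same section calls the study a feasibility study without formal hypothesis tests.

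**The concern.** A non-inferiority margin is the largest loss of patency that would still be acceptable. Scarce literature does not tell us what that loss is. Nor does setting one lower confidence limit against another: it gives no interval for the difference between device and surgery, so it cannot bound the deficit.

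The rule in Section 11.1 also has no term for the control's sampling error, although the plan prints a control interval 22 points wide (68.0% to 90.1%). If the result is reported in the terms of Section 11.2, a trial that has beaten 70% could be presented as statistically non-inferior to surgery within 10 points. The 5% error rate belongs to the first statement only. This affects the main conclusion drawn from the primary performance endpoint.

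**Working it through.** **Inputs.** One-sided alpha 0.05, power 80%, device rate 85%, margin 10 points, n=100 (Section 11.2). One-sided 95% Score bound against 70% (Section 11.1). Bypass rows of Table 11-2, at risk/events: 50/2, 48/3, 44/4.

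**1. The plan's own sample sizes.** n = [(1.645·√(p0(1-p0)) + 0.842·√(p1(1-p1)))/(p1-p0)]², with p1 = 0.85.
- p0 = 0.75: 102.6, so 103, as stated.
- p0 = 0.70: 49.4, so 50, the figure given for stent grafts.

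The 103 therefore belongs to a 75% goal, not to the 70% in the rewritten hypotheses.

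**2. What the 70% rule does at n=100.** The Score lower bound is 69.4% at 77/100 and 70.5% at 78/100, so 78 is the smallest pass. Exact binomial P(X≥78) is:
- 4.8% at a true 70%
- 10.1% at a true 71.8%
- 28.6% at a true 75%
- 97.8% at a true 85%

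**3. Distance of the goal from surgery.** 81.8 - 70 = 11.8 points from the observed rate; 85 - 70 = 15 points from the rate in the formula. Both exceed the stated 10.

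**4. Control standard error (Greenwood).**
- S = (48/50)(45/48)(40/44) = 0.818.
- Sum of d/[n(n-d)] = 2/(50·48) + 3/(48·45) + 4/(44·40) = 0.00449.
- SE = 0.818·√0.00449 = 0.055. The printed interval, back-calculated on the log-log scale, also gives 5.5 points.

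**5. Difference from bypass with both errors counted.** Lower bound = (p - 0.818) - 1.645·√(p(1-p)/100 + 0.055²).

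| Result | Difference (points) | One-sided 95% lower bound (points) |
|---|---|---|
| 78/100 | -3.8 | -15.1 |
| 82/100 | +0.2 | -10.8 |
| 83/100 | +1.2 | -9.7 |

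For 78/100 the combined SE is √(0.0414² + 0.0549²) = 0.0687, and -0.038 - 1.645·0.0687 = -0.151. Newcombe's method with 41/50 for the control gives -14.4. The margin is first met at 83/100 by either method.

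**6. How often a device exactly 10 points worse than surgery passes the 70% rule.**
- Surgery fixed at 81.8% (device 71.8%): 10.1%.
- Surgery at the formula's 85% (device 75%): 28.6%.
- Averaged over a true surgical rate distributed normally with mean 81.8% and SE 5.5 points: about 21%.

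**7. Effect of using 85% minus 10% as written.** Against a fixed 75% the smallest pass at n=100 is 83/100 (Score lower bound 76.0%), with exact power 76% at a true 85% and 99% at 90%.

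**The case against.** **Section 11.1 disclaims formal testing and states no surgical conclusion.** This softens the concern: the non-inferiority language is in the sample-size rationale, and the literal null hypothesis is patency of 70% or less. But Section 11.1 keeps the comparison with 70%, and Section 11.2 keeps the non-inferiority purpose, the hypotheses and the alpha. The permitted conclusion is left open.

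**Fixed performance goals are ordinary in single-arm device studies.** True, and the test is valid for the statement about 70%. The objection is only to the name given to the result.

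**Correcting the arithmetic to 75% removes the problem.** Most of the numerical gap does go: 83/100 is the smallest pass against 75% and also the smallest result meeting the margin in step 5. The match depends on this n and this control, however. A 75% goal would still ignore the control's error and rest on the same two reasons for the margin.

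**A reader might infer that imprecise surgical data lowered the bar, so that a smaller control study would lower it further.** The documents do not support this. The goal is a rate minus a fixed delta, and the same 10 points and 70% are used for the stent-graft comparison, which has more references and a different rationale (lesion diversity). The sentence on lower limits describes the goal; it does not compute it. The printed lower limit is 68.0%, not 70%.

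**Observed patency may make this moot.** Section 2.4 reports 90% at 6 months in 30 subjects. At a true 90% either threshold is passed at least 99% of the time. That lowers the practical risk but does not change what a pass means.

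**Conclusion.** The point holds as a limit on what may be concluded. Exceeding 70% does not establish non-inferiority to surgical bypass within 10 points: at 78/100 the plan's own control data leave a possible deficit of 15.1 points, and a device 10 points worse passes about 10% of the time with surgery fixed at 81.8%, or about 21% averaged over the control's uncertainty. Those two error rates answer different questions and should not be interchanged.

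The same care applies to power for an 83/100 threshold at a true 85%: 76% with the control held at its observed value, about 65% if control sampling is averaged over as well.

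Assumptions: all 100 subjects evaluable (with available data only, the smallest pass is 74/95 or 71/90, a similar percentage); the Table 11-2 arm stands for surgery; and the two populations are exchangeable. The calculation ignores between-study differences and the clustering of that study's 100 limbs in 86 patients. Allowing for these would probably widen the interval.

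**What to change.** 1. In Sections 11.1 and 11.2, state that passing means *the 70% performance goal was exceeded*, and that this is not a finding of non-inferiority to surgical bypass. Remove the sentence comparing lower limits as a description of a non-inferiority test. Do not offer scarce literature as the reason for the margin.
2. Reconcile 85% minus 10% with the 70% goal. If 75% is intended, 83/100 is needed and power at a true 85% is 76%, below the planned 80%, with no allowance for loss ("since no loss to follow-up is expected in the study, a sample size of 100 subjects should be sufficient"). If 70% is intended, drop the 85% formula and the 103 derived from it.
3. If a comparison with surgery is still reported, give the difference from 81.8% with an interval that includes the control's SE of about 5.5 points, labelled as an unadjusted historical comparison. This analysis is optional; items 1 and 2 are not.

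Cost: wording, plus one calculation from figures already printed; no new data. The real price is that the surgical non-inferiority claim is dropped or becomes harder to make.

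### The surgical-bypass goal is defined, and the 103 subjects sized, at 75%, but the hypotheses and the only stated comparison use 70%

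*Combined protocol and SAP*

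**What the plan says.** Section 11.2 gives two justifications for the sample size.

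- **Stent-graft comparison:** control 80%, margin 10 points, goal 70%, assumed true patency 85%, 50 subjects required, 60 enrolled.
- **Surgical-bypass comparison:** this is the stated reason for going from 60 to 100. From the literature the plan concludes that a "6-month surgical bypass primary patency rate of 82-85% can be extrapolated". It continues with "As such using as historical control rate of 80-85% and a non-inferiority margin of 10" percent.

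The surgical text then gives the goal as a formula, "\pi_{PG_performance} = 85\% \text{ historical control rate} - 10\% \text{ Delta", which is 75%. It rewrites the null hypothesis as "H_0: \pi_{PQB_performance} \leq 70" percent, identical to the stent-graft null. The same part says that the margin sets up a comparison "to the lower 95% CI reported for the competitive products (~70" percent), a sentence that also appears in the stent-graft part.

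For the surgical sizing, "the maximum sample size required is 103 subjects", and "since no loss to follow-up is expected in the study, a sample size of 100 subjects should be sufficient".

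The only comparison to be carried out is in section 11.1: "The lower bound of the one-sided 95% CI will be compared to the performance goal of 70" percent, which is explained there as 80% less 10 points. Nowhere does the plan compare the bound with 75%. Section 11.1 also calls the trial a feasibility study without formal hypothesis tests or a required sample size, whereas section 11.2 says that the size was chosen to show non-inferiority.

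**The concern.** The surgical goal has two values a few lines apart. One drives the number of subjects and the other drives the conclusion.

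The extra 40 subjects are justified in 11.2 by surgical results being better than stent-graft results, so the surgical benchmark should set a higher bar. It does not, because the full cohort is judged against the stent-graft goal. A result that clears 70% but not 75% would meet the written comparison and could be reported as non-inferior to surgical bypass, with a margin wider than the 10 points the plan claims.

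**Working it through.** **Inputs.** Assumed true patency p1 = 85%, one-sided alpha 0.05, power 80%, margin 10 points and surgical rate 82–85% (all 11.2); one-sided 95% score bound (11.1); 100 subjects (11.2).

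**1. Reproduce the plan's sample sizes.** One-sample test of a proportion with the null variance under H0:

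n = [(1.645·√(p0(1−p0)) + 0.8416·√(p1(1−p1))) / (p1−p0)]²

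| Goal p0 | Calculation | n | Plan's figure |
|---|---|---|---|
| 70% | [(0.7538 + 0.3005)/0.15]² = 49.4 | 50 | 50 (stent graft) |
| 72% | [(0.7385 + 0.3005)/0.13]² = 63.9 | 64 | none |
| 75% | [(0.7122 + 0.3005)/0.10]² = 102.6 | 103 | 103 (surgical) |

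The formula also returns the other distinct entries of Tables 11-1 and 11-3 (30, 38, 69, 174, 368, 1371). So 103 is the size for a 75% goal. In Table 11-3 a control of 85% tested at 70% falls in the 15% margin column, which shows 50; the 10% column shows 103.

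**2. Which goals follow from the plan's surgical rate?** 82% − 10 = 72% and 85% − 10 = 75%. No value between 82% and 85% gives 70%. Only the 80% end of the range in the lead-in sentence does, and that lies below the surgical range the plan extrapolates.

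**3. Patent grafts needed out of 100.** Score lower bound: 77 gives 0.694 and 78 gives 0.705; 82 gives 0.749 and 83 gives 0.760. So 70% needs 78 and 75% needs 83 (72% needs 80). Results of 78 to 82 clear the stated comparison and miss the defined surgical goal.

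**4. Chance of passing the 70% comparison when patency is only at the non-inferiority limit.** Exact binomial P(X ≥ 78), n = 100:

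| Control rate | Limit (control − 10) | Effective margin at a 70% goal | Chance of passing |
|---|---|---|---|
| 80% | 70% | 10 points | 4.8% |
| 81.8% (surgical 6-month figure, Table 11-2) | 71.8% | 11.8 points | 10.1% |
| 82% | 72% | 12 points | 10.8% |
| 85% | 75% | 15 points | 28.6% |

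With a 75% comparison, the last figure would be 3.8%.

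**5. Power at a true 85% against the 75% goal.**

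| Evaluable | Needed | Exact | Plan's approximation |
|---|---|---|---|
| 103 | 85 | 80.3% | 80.2% |
| 100 | 83 | 76.3% | 79.0% |
| 95 (assumed 5% loss) | 79 | 74.7% | 76.9% |
| 90 (assumed 10% loss) | 75 | 73.0% | 74.6% |

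The loss rates are my assumptions; the plan expects none. Against 72%, power with 100 is 93.4% exact (94.2% approximate), so the shortfall arises only at 75%. If true patency is 90%, the interim figure in section 2.4, power against 75% with 100 evaluable is 99.0%.

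**The case against.** The best defence is that the documents do not force 75%. The lead-in range includes 80%, which gives 70%. The plan also offers a separate reason for 70%, the lower confidence limit of competing products, and Table 11-2 does show a 6-month surgical lower limit of 0.680. The tabulated surgical rate is 81.8%, and 103 is called a maximum, so 85% might be read as a worst case for sizing only. On that reading 28.6% is the extreme case.

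Part of this stands. The 28.6% does require a control of exactly 85%, and a documented choice of 82% would be coherent. But that choice gives a goal of 72% and 64 subjects, not 70%, and even there the chance of passing at the limit is about twice nominal. The lower-limit argument agrees with neither the written formula nor the 103. A control of 80% would require only 50 subjects and remove the reason for the increase.

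A second defence is that 11.1 disclaims formal testing and does not say what follows from the comparison. That limits the consequence if no surgical claim is ever made. It does not remove the inconsistency, because 11.2 states hypotheses, alpha, power and a non-inferiority aim.

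Finally, the power gap is small by the plan's own formula (79.0% against 80%), and the exact figure is lower partly because the cut-off of 83 has a true size of 3.8%. That is fair. The threshold is the main defect and the power figure is secondary.

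**Conclusion.** The plan is wrong as written and must be corrected: the surgical goal is 75% by formula and by sample size, but 70% in the hypotheses and in the only comparison. Meeting 70% would support a conclusion against the stent-graft benchmark. It would not show non-inferiority to surgery within 10 points at any control rate in the plan's 82–85% range; the effective margin there is 12 to 15 points. The error rate at the limit is 10.8% to 28.6% instead of 5%.

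These figures assume 100 evaluable subjects, the score bound named in 11.1, and that a surgical non-inferiority conclusion would be drawn from the 70% comparison.

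**What to change.** **Main route.**

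- In the surgical part of 11.2, state H0 as at most 75% and HA as above 75%, and reconcile the sentence about the competitors' lower limit with the 85% minus 10 formula.
- In 11.1, make any conclusion of non-inferiority to surgical bypass depend on the full-cohort lower bound exceeding 75%, and limit a conclusion from the 70% goal to the stent-graft benchmark.
- Use the same full-cohort bound for both and add no separate test at 60 subjects. The two conclusions are nested (83/100 implies 78/100), so no alpha adjustment is needed.
- Restate power for 100 evaluable subjects against 75% as about 76% exact (79% by the plan's formula), and give the figure under a stated loss assumption.

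**Alternative.** Keep 70% and remove the 85% formula, the 103 and the surgical non-inferiority claim.

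**Either way**, reconcile the statement in 11.1 that there is no formal testing with 11.2: remove it, or drop the non-inferiority claim.

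**Cost.** This is a text change in 11.1 and 11.2 with no added patients. The main route raises the surgical hurdle from 78 to 83 of 100. It alters a primary criterion after interim results were seen (section 2.4), so it should be disclosed as such and handled under section 16.3. Because it raises the bar, it does not favour the sponsor.
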